### **8.1 Efficacy Assessments**

To evaluate the efficacy of ETC-1002, blood samples for LDL-C, non-HDL-C, TC, HDL-C, TG, apo B, hsCRP, and HbA1c will be collected.

The investigator or subinvestigator will instruct subjects to visit the trial site according to the schedule specified in Table 1.3-1 under fasting conditions and collect blood samples. The investigator or subinvestigator will record the date and time of blood sampling and the fasting state at the time of blood sampling in the source document and the eCRF. The test results will be directly reported to the sponsor by the central laboratory selected by the sponsor in electronic files. Therefore, it is not necessary to record the results in the source document and eCRF. The fasting state is defined as a state in which a subject has fasted (including abstaining from sugar-containing beverages such as juice) for 10 hours or more. If a subject cannot visit the trial site in a fasting state, the subject should visit the trial site again in a fasting state for blood sampling within the visit window for the same evaluation time point. If the subject cannot visit in the fasting state again within the visit window for the same evaluation time point, this case will be recorded as a protocol deviation and the blood sample will be submitted as a sample in a fed state to the central laboratory. Each subject will visit the trial site without taking the IMP on the visit day.

Samples will be sent to the central laboratory, the results of which will be used for analysis. LDL-C values will be measured using the direct method and calculated using the Friedewald formula ( $TC - HDL - C - TG/5$ ). Proper sample collection, handling, and shipping procedures will be provided to the trial sites in a separate manual prior to the start of the trial.

To maintain the blind of the trial, the test results will not be reported to the trial sites and the sponsor for the blind items at Week -4 and Day 1 in the rollover subjects from the phase 3 confirmatory trial (Protocol No. 346-102-00002). The test results will be stored strictly by the central laboratory, disclosed to the trial site after unblinding in the phase 3 confirmatory trial (Protocol No. 346-102-00002), and provided to the sponsor in electronic files.

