## 10.2 Appendix 2: Clinical Laboratory Tests

The tests detailed in Table 10.2-1 will be performed.

Table 10.2-1 Clinical Laboratory Assessments	
Hematology: Red blood cell count Hemoglobin Hematocrit Mean corpuscular hemoglobin concentration Mean corpuscular volume White blood cell (WBC) count WBC count with differential (neutrophils, eosinophils, basophils, monocytes, and lymphocytes) Platelets  Urinalysis (parameters other than pH and specific gravity will be included in the qualitative urinalysis) pH Protein Glucose Occult blood Bilirubin Urobilinogen Specific gravity Ketones	Serum Chemistry: Alkaline phosphatase ALT AST Total bilirubin Gamma glutamyl transferase Total protein Albumin Lactate dehydrogenase Blood urea nitrogen Creatinine Uric acid CK Serum electrolytes (sodium, potassium, chloride, calcium, bicarbonate) Glucose*

\*Testing will be performed in the fasting state.

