3.4 Trial Visit Window

For the efficacy and safety endpoints (except for AEs), acceptable windows of analysis visits will be set, and the analysis will be based on the analysis visits, regardless of the time points recorded in the case report form (CRF). Analysis visits will be specified based solely on fasting data for non-HDL-C, TC, HDL-C, TG, and LDL-C (calculated using the Friedewald formula) among the fasting lipid parameters for the efficacy endpoints. The handling of fasting data is described in [Section 5.3](#).

Acceptable windows of analysis visits are shown in [Table 3.4-1](#). The start day of investigational medicinal product (IMP) administration is defined as Day 1. Baseline is defined as the last data before the start of IMP administration. If multiple data points are available for a certain acceptable window, the last data point will be used for the analysis. Data collected more than 2 days after the last IMP administration will be excluded. The last data obtained between the initial IMP administration and 2 days after the last IMP administration will be defined as the Last Visit.

Table 3.4-1 Acceptable Windows of Analysis Visits	
Week	Trial Day Interval
Baseline	- 1
Week 4	2 - 43
Week 8	44 - 71
Week 12	72 - 99
Week 16	100 - 127
Week 20	128 - 155
Week 24	156 - 183
Week 28	184 - 211
Week 32	212 - 239
Week 36	240 - 267
Week 40	268 - 295
Week 44	296 - 323
Week 48	324 - 351
Week 52	352 - 375
Last Visit	Last data obtained between the initial IMP administration and 2 days after the last IMP administration in the treatment period
Week 56 (FU)	Time point recorded in the CRF

4 Sample Size

Assuming a withdrawal of approximately 20 subjects during the treatment period, the target number of subjects is set at 120 to ensure that 100 subjects will complete the 1-year treatment to assess the safety of ETC-1002 at 180 mg in long-term administration.

5 Statistical Analysis Datasets

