5.3 Handling of Missing Data

Missing data will not be imputed.

Fasting lipid parameters will be handled as shown in the table below with regard to fasting conditions.

Fasting Lipid Parameters	Handling of Data
LDL-C (direct method)	Parameter to be used in the analysis, irrespective of fasting conditions
non-HDL-C, TC, HDL-C, TG, LDL-C (Friedewald formula)	Parameters to be used in the analysis only when obtained under fasting conditions

6 Primary and Secondary Outcome Variables

There are no primary or secondary outcome variables.

7 Disposition and Demographic Analysis

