8.3 Subgroup Analyses

Subgroup analyses will be performed by the following items for the percent change in LDL-C (direct method) from baseline at Weeks 24 and 52. Statin intensity categories and types are shown in [Appendix 6](#). In the data for each statin type, subjects who use multiple medications will be excluded from the summarization.

- Statin response (inadequate response to statins/difficulties in treatment with statins)
- Sex (Male, Female)
- Familial hypercholesterolemia (Yes, No)
- Diabetes mellitus (Yes, No)
- Age (<65 years, ≥65 years and <75 years, ≥75 years)
- Statin use (Yes, No)
- BMI (<25 kg/m², ≥25 kg/m² and <30 kg/m², ≥30 kg/m²)
- eGFR (<60 mL/min/1.73 m², ≥60 mL/min/1.73 m² and <90 mL/min/1.73 m², ≥90 mL/min/1.73 m²)
- LDL-C at baseline (<100 mg/dL, ≥100 mg/dL and <120 mg/dL, ≥120 mg/dL and <140 mg/dL, ≥140 mg/dL)
- Statin intensity (Low-intensity statins, High-intensity statins, No statins)
- Statin type (atorvastatin calcium trihydrate, fluvastatin sodium, pitavastatin calcium, pravastatin sodium, rosuvastatin calcium, simvastatin, no statins)

9 Safety Analyses

For the safety analysis set, the summarization will be performed by rollover, newly enrolled, and overall subjects. Baseline is defined as the last data before the start of IMP administration. The analysis visits will be Weeks 4, 8, 12, 16, 20, 24, 28, 32, 36, 40, 44, 48, and 52, unless otherwise specified. The same analysis will be performed for each statin response (inadequate response to statins/difficulties in treatment with statins). Summarization at the Last Visit will also be performed in addition to summarization at each time point.

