9.3 Clinical Laboratory Data

Among the urinalysis parameters in laboratory tests, those other than pH and specific gravity will be included in the qualitative urinalysis.

For parameters other than the qualitative urinalysis, descriptive statistics of the actual value and change from baseline will be calculated at each time point. For qualitative urinalysis parameters, shift tables at each time point from baseline will be prepared. For parameters other than qualitative urinalysis, measured values will be categorized using

the reference range to “below the lower limit of reference range,” “within the reference range,” and “above the upper limit of reference range,” and shift tables at each time point from baseline will be prepared.

The number and percentage of subjects meeting the criteria for identifying laboratory values of potential clinical relevance ([Appendix 2: Criteria for Identifying Laboratory Values of Potential Clinical Relevance](#)) and Hy’s law ([Appendix 7: Criteria for Hy’s Law](#)) after IMP administration will be calculated. All data obtained after IMP administration during the treatment period will be analyzed, including those obtained at unscheduled visits.

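### The SAP 9.3 by-visit glucose statistics and shift tables can mix fed and fasting samples, because the SAP's fasting-only rule names five lipid parameters but not glucose

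*SAP*

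**What the plan says.** **Glucose is meant to be fasting.** In Protocol Table 10.2-1 (section 10.2) the glucose entry carries a footnote: "Testing will be performed in the fasting state". Protocol 8.7.1 asks for at least 10 hours of fasting before the safety laboratory draw and has the fasting state recorded in the eCRF.

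**Fed samples have a route to the laboratory.** Protocol 8.1, written for the efficacy samples, covers a subject who cannot attend fasting and cannot return fasting within the visit window. The case is a protocol deviation, and "the blood sample will be submitted as a sample in a fed state to the central laboratory".

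**The fasting rule is limited to lipids.** SAP 3.4 states: "Analysis visits will be specified based solely on fasting data for non-HDL-C, TC, HDL-C, TG, and LDL-C (calculated using the Friedewald formula"). SAP 5.3 gives the same five parameters the instruction "Parameters to be used in the analysis only when obtained under fasting conditions". Direct LDL-C is used whatever the fasting state. Glucose appears in neither place.

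**The glucose outputs have no such rule.** SAP 9.3 applies to glucose as to other quantitative laboratory parameters: "descriptive statistics of the actual value and change from baseline will be calculated at each time point", and, by position against the reference range, "shift tables at each time point from baseline will be prepared". On which value is used, SAP 3.4 says: "If multiple data points are available for a certain acceptable window, the last data point will be used for the analysis". The opening of SAP section 9 says: "Baseline is defined as the last data before the start of IMP administration". Protocol 9.4.2.2 describes the same summaries, also without a fasting condition.

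**One glucose output does separate the two states.** SAP Appendix 2 flags high glucose at 126 mg/dL or more when fasting and at 200 mg/dL or more when not fasting.

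**The concern.** The SAP recognises that fed and fasting glucose need different yardsticks, and applies that only to the count of potentially clinically relevant values. The means, changes from baseline and shift tables in the same section use whatever value comes last in the window.

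Two things are at stake. First, a difference in fed share between baseline and a later visit moves the mean change for a reason unrelated to the drug. Safety is the primary objective, laboratory tests are among its endpoints, and the trial has no control arm in which the same artefact would appear and could be netted out. Second, the shift table compares single values within a subject. A fed value on one side of the comparison can put that subject in the wrong cell, whatever happens on average.

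The last-value rule adds another route. Protocol 8.8.1 lets investigators repeat laboratory tests. If a repeat that includes glucose is drawn fed later in the same window, it displaces a valid fasting result. The five lipid parameters are protected from this; glucose is not.

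**Working it through.** The plan states no figure for fed samples or for the effect of a meal on glucose, so there is none to reproduce. The check is a comparison of the rules, followed by an illustration on assumed inputs.

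**1. Which rule governs each output**

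| Output | Fasting condition in the SAP |
|---|---|
| TG, TC, HDL-C, non-HDL-C, Friedewald LDL-C | Fasting values only (3.4, 5.3) |
| Direct LDL-C | Any value, stated explicitly (5.3) |
| Glucose, Appendix 2 high criterion | Separate cut-offs, 126 and 200 mg/dL |
| Glucose, by-visit statistics (9.3) | None |
| Glucose, shift tables (9.3) | None |

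Nothing else in the SAP supplies a condition for the last two rows.

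**2. One subject followed through the rules (invented values)**

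Take a fasting 104 mg/dL on Day 1 and a fed 168 mg/dL at Week 24.
- Change from baseline: 168 − 104 = +64 mg/dL, which enters the Week 24 mean.
- Shift table: above range if 168 exceeds the laboratory's upper limit, which the documents do not give.
- Appendix 2: 168 < 200, so not flagged.

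The same value is treated as unremarkable in one table and as a 64 mg/dL rise in another. Reverse the two samples and the change is −64 mg/dL.

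**3. Effect on the mean change**

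Let f_visit and f_base be the fed shares at the visit and at baseline, and d the average fed increment, taken as the same at both times:

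bias = (f_visit − f_base) × d

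Assumed ranges, not from the documents: fed share 2-10%, d = 10-60 mg/dL.

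| f_visit | f_base | d (mg/dL) | Bias (mg/dL) |
|---|---|---|---|
| 0.02 | 0 | 10 | 0.02 × 10 = +0.2 |
| 0.05 | 0 | 40 | 0.05 × 40 = +2.0 |
| 0.10 | 0 | 60 | 0.10 × 60 = +6.0 |
| 0.05 | 0.05 | 10-60 | 0 |
| 0 | 0.05 | 10 | −0.05 × 10 = −0.5 |
| 0 | 0.05 | 40 | −0.05 × 40 = −2.0 |

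The sign depends on which side has more fed samples, and equal shares give no net bias.

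**4. Smaller tables**

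SAP section 9 repeats the safety summaries by statin response. Protocol section 5 plans at least 20% of subjects with difficulty in treatment with statins: 0.20 × 120 = 24. In a group of 24, one fed value with an assumed increment of 40 mg/dL moves the mean by 40 / 24 = 1.7 mg/dL.

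**5. Number of values involved**

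With 120 subjects, 13 post-baseline visits and no dropout there are 120 × 13 = 1,560 glucose values. A fed share of 2% is 0.02 × 1,560 ≈ 31 of them; 10% is 156.

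**6. Shift tables**

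No misclassification rate can be derived: the documents give neither the reference limits for glucose nor its distribution. Cancellation between subjects does not help here, because each cell counts individuals.

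**The case against.** **The fed route to glucose is not stated.** Protocol 8.1 covers efficacy samples, and glucose is not among them. Protocol 8.7.1, which does govern the chemistry panel, requires fasting and has no provision for submitting a fed sample. The non-fasting cut-off in Appendix 2 could exist only for unscheduled visits, which SAP 9.3 expressly includes in that count. This stands as a limit on the evidence. That fed glucose values will occur is an inference from the shared visits, the recording of fasting state in 8.7.1, and the Appendix 2 cut-off.

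**Fed samples should be few.** Subjects are told to attend fasting. Under 8.1 a non-fasting subject is to return within the window, and a fed sample is a deviation. This also stands, although the SAP thought such samples likely enough to write a rule for lipids.

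**Summarising every observed safety value is a defensible default.** In general it is. It is weaker for a test that the protocol defines as fasting, in an SAP that already treats fed values separately for five other analytes and, in one table, for glucose itself.

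**Stronger readings to avoid.** A reader might infer that the plan will report fed samples as a glucose rise under ETC-1002. The documents do not support that: the error can go either way, it cancels in the mean change when fed shares are equal, and nothing shows that any fed glucose value exists. A reader might also infer that the diabetes findings as a whole are compromised. They are not. The diabetes- and hypoglycemia-related events of special interest are defined by preferred term in SAP Appendix 5, HbA1c is a separate measure, and the Appendix 2 high-glucose criterion is already split by fasting state.

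**Conclusion.** The gap holds in a limited form. As written, the SAP allows non-fasting glucose into the 9.3 descriptive statistics and shift tables, contrary to the protocol's definition of the test and out of line with the SAP's own handling of lipids. The consequence is that these tables can be distorted in either direction.

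The size is unknown. The 0.2-6 mg/dL range for the mean change assumes a fasting baseline for everyone, a fed share of 2-10% at the visit and an increment of 10-60 mg/dL, none of which comes from the documents. No figure can be put on the shift tables. The affected outputs are descriptive, with no test or decision rule attached. This is a worthwhile tidy-up, not a threat to the trial's conclusions.

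**What to change.** Add glucose to the fasting-only parameters in SAP 3.4 and 5.3, for use in the 9.3 descriptive statistics and shift tables. Apply it at baseline (last fasting value before the first dose), at each post-baseline visit (last fasting value in the window) and at the Last Visit. Keep non-fasting values in the Appendix 2 count, which has a cut-off for them, and in the listings. A footnote giving the number of values left out at each visit would let the reader judge the loss.

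The cost is a line or two in the SAP. Fasting status is already in the eCRF, so no new data are needed and no trial procedure changes. A few glucose values drop out of these tables, as does change from baseline for any subject with no fasting baseline. Because the SAP 3.4 baseline window has no stated lower bound before Day 1, an earlier fasting pre-dose sample could serve, which keeps that loss small. If the sponsor prefers to drop nothing, showing fasting and non-fasting glucose separately would also resolve the point.

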### 5.2.2 Exclusion Criteria

Subjects will be excluded if they meet any of the following exclusion criteria when assessed:

- Newly Enrolled Subjects
  - 1) Females who are pregnant or breast-feeding, or who have a positive pregnancy test (urine) result at screening (Week –2) or on Day 1
  - 2) Sexually active and reproductive males or sexually active females of childbearing potential, who do not agree to practice 2 different approved methods of birth control or to maintain complete abstinence (the methods of periodic abstinence and withdrawal are not appropriate for contraception) during the trial and for 30 days after final IMP administration. If employing birth control, 2 of the following methods must be used: vasectomy, tubal ligation, intrauterine device, birth control pill, or condom (all methods are approved or certified in Japan).
  - 3) Patients with homozygous familial hypercholesterolemia (HoFH)

- 4) Patients who currently have or who have had within the past 3 months prior to screening any of the following cardiovascular diseases, or those who had developed any of the following AEs during the screening period
  - Myocardial infarction, severe or unstable angina pectoris, coronary angioplasty, coronary artery bypass graft, stroke, transient ischemic attack, symptomatic carotid artery stenosis, symptomatic peripheral arterial disease, or decompensated heart failure
  - Abdominal aortic aneurysm
  - Patients with risk factors for torsade de pointes, such as unexplained syncope or long-QT syndrome, or a family history of long-QT syndrome
- 5) Patients with uncontrolled hypertension, defined as follows: sitting systolic blood pressure of  $\geq 160$  mmHg or diastolic blood pressure of  $\geq 100$  mmHg after resting 5 minutes at screening (Week -2)
- 6) Patients with uncontrolled and serious hematologic or coagulation disorders or with hemoglobin of  $< 10.0$  g/dL at screening (Week -2)
- 7) Patients with uncontrolled diabetes with HbA1c of  $\geq 9\%$  at screening (Week -2)
- 8) Patients with uncontrolled hypothyroidism with thyroid-stimulating hormone (TSH) of  $> 1.5 \times$  the upper limit of normal (ULN) at screening (Week -2)
- 9) Patients with a liver disease or dysfunction, including:
  - Positive serology for hepatitis B surface antigen (HBsAg) or a positive hepatitis C virus (HCV) antibody test at screening (Week -2)

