Appendix 2 Criteria for Identifying Laboratory Values of Potential Clinical Relevance

Laboratory Tests	Criteria
Chemistry	
AST	$\geq 3 \times$ upper limit of normal (ULN)
ALT	$\geq 3 \times$ ULN
Bilirubin, Total	$\geq 2 \times$ ULN
ALP	$\geq 3 \times$ ULN
Urea nitrogen	≥ 30 mg/dL
Creatinine	≥ 2.0 mg/dL
Creatine kinase (CK)	$\geq 4 \times$ ULN
Uric acid	≥ 9 mg/dL
Hematology	
Hematocrit	Males: $\leq 37\%$ and ≥ 3 percentage points decrease from baseline Females: $\leq 32\%$ and ≥ 3 percentage points decrease from baseline
Hemoglobin	Males: ≤ 11.5 g/dL Females: ≤ 9.5 g/dL
Leukocyte count	$\leq 2,800 \times 10^6/L$
Leukocyte count	$\geq 16,000 \times 10^6/L$
Platelet count	$\leq 7.5 \times 10^{10}/L$
Platelet count	$\geq 70 \times 10^{10}/L$
Urinalysis	
Protein	Increase of ≥ 2 units
Glucose	Increase of ≥ 2 units
Additional criteria	
Chloride	≤ 90 mEq/L
Chloride	≥ 118 mEq/L
Potassium	≤ 2.5 mEq/L
Potassium	≥ 6.5 mEq/L
Sodium	≤ 126 mEq/L
Sodium	≥ 156 mEq/L
Calcium	≤ 8.2 mg/dL
Calcium	≥ 12 mg/dL
Glucose	Fasting: ≥ 126 mg/dL Non-Fasting: ≥ 200 mg/dL
Glucose	≤ 50 mg/dL
Total cholesterol	≥ 240 mg/dL
LDL cholesterol	≥ 160 mg/dL
HDL cholesterol	< 40 mg/dL
Triglycerides, Fasting	≥ 150 mg/dL

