CT-8.18-9	Incidence of IMP-related TEAEs by MedDRA System Organ Class and Preferred Term by Baseline Statin Medication (Safety Analysis Set)
CT-8.19	Incidence of AESIs by MedDRA System Organ Class and Preferred Term by eGFR (Safety Analysis Set)
CT-8.20	Incidence of IMP-related AESIs by MedDRA System Organ Class and Preferred Term by eGFR (Safety Analysis Set)
CT-9.1	Listing of Deaths (Safety Analysis Set)

- CT-9.2 Listing of Serious Adverse Events Other Than Death (Safety Analysis Set)
- CT-9.3 Listing of Discontinuations Due to Adverse Events (Safety Analysis Set)
- CT-10.1.1-1 Descriptive Statistics for Clinical Laboratory Test Results - Serum Chemistry (Safety Analysis Set)
- CT-10.1.1-2 Descriptive Statistics for Clinical Laboratory Test Results by Statin Response - Serum Chemistry (Safety Analysis Set)
- CT-10.1.2-1 Descriptive Statistics for Clinical Laboratory Test Results - Hematology (Safety Analysis Set)
- CT-10.1.2-2 Descriptive Statistics for Clinical Laboratory Test Results by Statin Response - Hematology (Safety Analysis Set)
- CT-10.1.3-1 Descriptive Statistics for Clinical Laboratory Test Results - Urinalysis (Safety Analysis Set)
- CT-10.1.3-2 Descriptive Statistics for Clinical Laboratory Test Results by Statin Response - Urinalysis (Safety Analysis Set)
- CT-10.2.1-1 Shift Tables of Clinical Laboratory Test Results - Serum Chemistry (Safety Analysis Set)
- CT-10.2.1-2 Shift Tables of Clinical Laboratory Test Results by Statin Response - Serum Chemistry (Safety Analysis Set)
- CT-10.2.2-1 Shift Tables of Clinical Laboratory Test Results - Hematology (Safety Analysis Set)
- CT-10.2.2-2 Shift Tables of Clinical Laboratory Test Results by Statin Response - Hematology (Safety Analysis Set)
- CT-10.2.3-1 Shift Tables of Clinical Laboratory Test Results - Urinalysis (Safety Analysis Set)
- CT-10.2.3-2 Shift Tables of Clinical Laboratory Test Results by Statin Response - Urinalysis (Safety Analysis Set)
- CT-10.2.4-1 Shift Tables of Clinical Laboratory Test Results - Qualitative Urinalysis (Safety Analysis Set)
- CT-10.2.4-2 Shift Tables of Clinical Laboratory Test Results by Statin Response - Qualitative Urinalysis (Safety Analysis Set)

CT-10.3-1	Incidence of Potentially Clinically Significant Abnormalities in Laboratory Tests (Safety Analysis Set)
CT-10.3-2	Incidence of Potentially Clinically Significant Abnormalities in Laboratory Tests by Statin Response (Safety Analysis Set)

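### In 27 of 30 rows the laboratory relevance criteria ignore baseline, so incidence table CT-10.3 mixes abnormalities present before dosing with new ones

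*SAP*

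**What the plan says.** SAP 9.3 plans "The number and percentage of subjects meeting the criteria for identifying laboratory values of potential clinical relevance" after IMP administration, and adds: "All data obtained after IMP administration during the treatment period will be analyzed, including those obtained at unscheduled visits". It limits neither the numerator nor the denominator by baseline status. The output is CT-10.3-1, "Incidence of Potentially Clinically Significant Abnormalities in Laboratory Tests (Safety Analysis Set", with a version by statin response.

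The cut-offs are in SAP Appendix 2, "Criteria for Identifying Laboratory Values of Potential Clinical Relevance". Hematocrit needs a low value "and ≥ 3 percentage points decrease from baseline". Urine protein and urine glucose are each defined by "Increase of ≥ 2 units". All other rows are absolute values, for example glucose: "Fasting: ≥ 126 mg/dL Non-Fasting: ≥ 200 mg/dL".

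The two companion tables work differently. Appendix 1 (vital signs) and Appendix 3 (ECG) require both a threshold value and a minimum change from the subject's own baseline; body weight is judged on change alone. Protocol 8.8.1 applies the same principle to adverse events: one continuing from baseline is treatment-emergent only if it worsened.

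**The concern.** A subject who is over a fixed cut-off before the first dose, and over it again at any one later visit, is counted in CT-10.3 as a post-treatment abnormality. A subject who newly crosses the cut-off is counted in the same cell. The title says incidence, but the number is a mixture of prevalence and new onset.

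This matters here because safety is the primary objective and no control arm shows the background level. Several affected rows also concern parameters that the protocol singles out: uric acid (2.3 and 8.7.1) and hemoglobin, creatinine and urea nitrogen (8.7.1). A high count in these rows could be read as a drug effect when part of it was there at baseline.

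**Working it through.** **Design figure.** 100 completers + about 20 withdrawals = 120 treated (SAP 4). This reproduces and is not in dispute; 120 serves below as the denominator.

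**Row count in Appendix 2.**

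| Block | Fixed cut-off | Refers to a change |
|---|---|---|
| Chemistry | 8 | 0 |
| Hematology | 5 | 1 (hematocrit) |
| Urinalysis | 0 | 2 (protein, glucose) |
| Additional | 14 | 0 |
| Total | 27 | 3 |

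27/30 = 90% of rows. By analyte it is 20 of 23 (87%).

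**Cut-offs against entry rules (Protocol 5.2.1 and 5.2.2).**

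| Parameter | Counted if | Entry rule | Can be met at entry? |
|---|---|---|---|
| Fasting glucose | ≥126 mg/dL | Type 2 diabetes qualifies; no glucose limit; exclusion for "Patients with uncontrolled diabetes with HbA1c of" 9% or more (newly enrolled) | Yes |
| Triglycerides | ≥150 mg/dL | <400 mg/dL at Week −2 (newly enrolled) | Yes, 150 to <400 |
| LDL-C | ≥160 mg/dL | Floors of 100, 120 or 140 mg/dL; no ceiling | Yes |
| Uric acid | ≥9 mg/dL | None | Yes |
| Hemoglobin, men | ≤11.5 g/dL | <10.0 g/dL excluded | Yes, 10.0 to 11.5 |
| Hemoglobin, women | ≤9.5 g/dL | <10.0 g/dL excluded | Largely no |
| AST, ALT | ≥3×ULN | Same cut-off excluded | Largely no |
| Bilirubin | ≥2×ULN | Same cut-off excluded | Largely no |
| CK | ≥4×ULN | >3×ULN excluded, newly enrolled only | Largely no if newly enrolled; no rule for rollover |

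It is largely no, rather than no, because these checks are made at Week −2 (rollover: at or by Week 8 of the confirmatory trial), while baseline is the last value before dosing. Setting aside AST, ALT, bilirubin and CK, 27 − 4 = 23 of 30 rows (77%) have neither a baseline condition nor a comparable entry cap.

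**A treated improvement can be counted.** Take an assumed baseline LDL-C of 210 mg/dL and the phase 2 mean change at 180 mg of −21.26% (Protocol 2.1): 210 × (1 − 0.2126) = 165 mg/dL. That subject improves and still meets ≥160 mg/dL.

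**Size, for illustration only.** Let p be the share meeting a criterion at baseline, s the share of those meeting it again after dosing, and q the new-onset rate among the rest. None is given in the documents.

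Count as planned = 120·p·s + 120·(1 − p)·q. The second term is the new cases.

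With s = 0.9 and q = 5%:

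| p | Pre-existing | New | Count as planned | Pre-existing share |
|---|---|---|---|---|
| 5% | 5.4 | 5.7 | 11.1 (9.3%) | 49% |
| 10% | 10.8 | 5.4 | 16.2 (13.5%) | 67% |
| 20% | 21.6 | 4.8 | 26.4 (22.0%) | 82% |
| 40% | 43.2 | 3.6 | 46.8 (39.0%) | 92% |

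Over p 5–40%, s 0.7–1.0 and q 2–10%, the share runs from 4.2/(4.2 + 11.4) = 27% to 48/(48 + 1.44) = 97%.

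**Do the shift tables recover the split?** They classify values as below, within or above the reference range at each visit. Where the Appendix 2 cut-off lies beyond the reference limit, a subject just above range at baseline who later passes the cut-off appears as above to above, as does one who was past it all along. The protocol's laboratory panel (Table 10.2-1) does not list the lipids, so it is unclear whether those rows get a shift table at all.

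**The case against.** The case on the other side has four parts.

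1. **Other outputs adjust for baseline.** SAP 9.3 gives change from baseline and shift tables at each visit. CT-10.4 lists abnormal findings, the adverse events of special interest cover uric acid, hemoglobin, renal and diabetes terms, and the lipids are analysed by percent change in SAP 8. A reader might infer from CT-10.3 that neither a signal nor its absence can be read for these parameters. The documents do not support that. Adding pre-existing cases can only raise the count, so a low count still bounds the number of new cases from above. What stands is narrower: none of the summary tables shows how many subjects newly crossed an Appendix 2 cut-off.

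2. **The table does not report only pre-existing disease.** A reader might infer that it does. It counts both kinds, and entry rules protect several rows. This objection stands in full.

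3. **The magnitude rests on assumptions.** This also stands. In addition, repeated sampling will push some subjects with normal baselines over a cut-off by chance. That is a separate matter, and a baseline split would not remove it.

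4. **Excluding baseline-positive subjects could hide drug effects.** Rollover subjects' baseline is Week 12 of the double-blind confirmatory trial (Protocol Table 1.3-1, note b), when some may be on ETC-1002. Protocol 2.3 says uric acid rises within the first month and then stays stable. A stable drug-caused elevation would vanish from a count limited to baseline-negative subjects. This stands, and it means the present count should be supplemented, not replaced.

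**Conclusion.** The point holds for CT-10.3. The rule counts subjects without regard to baseline in 27 of 30 rows, it differs from the rule for vital signs and ECG, and the SAP gives no reason. The mixing is a practical matter for glucose, triglycerides, LDL-C, uric acid and male hemoglobin. It is small for AST, ALT, bilirubin and female hemoglobin, and for CK in newly enrolled subjects. The documents do not settle it for creatinine and the remaining rows.

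Its size cannot be computed from the documents; the 27% to 97% range depends wholly on the assumed p, s and q. This is a defect in how one safety table can be interpreted, and it does not undermine the laboratory analysis as a whole.

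**What to change.** In SAP 9.3 and CT-10.3, keep the present count and add for each criterion:

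- (a) the number and percentage meeting it after dosing among subjects who did not meet it at baseline, with those subjects as the denominator;
- (b) a row for subjects who met it at baseline.

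Present both separately for newly enrolled and rollover subjects, a split that SAP 9 already prescribes, and read the newly enrolled column as the cleaner estimate of new abnormalities. Do not drop rollover subjects who meet a criterion at baseline. Where the data are available, also classify rollover subjects against the confirmatory trial's pre-treatment baseline.

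The cost is SAP wording, some programming and extra table rows, with smaller denominators that differ by parameter. No new assessments of subjects are needed; the additional rollover classification needs pre-treatment values from the confirmatory trial.
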